9 STATISTICAL AND ANALYSIS ISSUES

9.1 Adjustments for Covariates

The categorical, randomization stratification variables sex (0 = male, 1 = female) and baseline HCe group (<40 mg/day and \geq 40 mg/day) will be used in all efficacy analyses. Additional categorical covariates may include baseline daily GC type (0 = short-acting, 1 = intermediate acting or combination) and CAH Type (0 =simple virilizing, 1=salt-wasting). Baseline daily GC dose in HCe or BSA adjusted dose may also be included as a continuous covariate. The baseline value of continuous efficacy endpoints will be included as a continuous covariate in statistical models, such mixed model repeated measures (MMRM), analysis of covariance (ANCOVA), or logistic regression.

9.2 Assessing Normality

Modest departures in the distribution of subject level data from Normality are of no consequence when sample size is high, for example, above a total $N \geq 10$, as Normality of the test statistics, e.g the difference in treatment group means, is assured by the Central Limit Theorem. When based on a total $N \geq 10$, the moment generating function for any test statistic derived from any underlying (non-Normal) probability distribution falls within less than 5% of the ideal moment generating function for the Standard Normal distribution, thus guaranteeing valid inference based upon the Normal approximation. This figure rises to within less than 2.5% of the ideal moment generating function with a total $N \geq 20$.

If, however, departures from Normality are encountered, especially when the effective sample size may be low, a supportive analysis may be performed based on rank values in place of original values.

9.3 Handling Dropouts or Missing Data

Every effort will be made by the Sponsor to ensure completeness of data collection. In the subject listings, all collected and all imputed values, if any, will be presented. However, and despite best efforts, some missing data are inevitable.

9.3.1 Handling of Efficacy Data

A sensitivity analyses will be conducted for the Primary Efficacy Endpoint and Secondary Efficacy Endpoints under the assumption of missing at random and missing not at random.

9.3.2 Handling of Laboratory Data

For laboratory data, a missing baseline value will be replaced with the last available assessment, generally the screening assessment. A retest value will be used if the first test is invalidated, e.g., specimen hemolyzed. For non-PK laboratory values that are continuous in nature but are presented as either above or below the respective quantitation limits, the following imputations will be made for the purposes of summarization:

- If value is listed as $< X$, then the imputed value will be $X/2$
- If a value is listed as $\leq X$, then the imputed value will be X
- If value is listed as $> X$, then the imputed value will be $X+1$
- If a value is listed as $\geq X$, then the imputed value will be X

9.3.3 Handling of Safety Data

9.3.3.1 Adverse Events

If the time of onset (before or after intake of study drug) cannot be determined whether an AE is treatment-emergent because of a partial onset date, the event will be counted as a TEAE.

Adverse events with incomplete start dates will be considered TEAEs, if:

- Day and month are missing and the year is equal to or after the year of the first date of study drug dosing;
- Month is missing and the year is equal to or after the year of the first date of study drug dosing;
- Day is missing and the year is equal to the year of the first date of study drug dosing and the month is equal to or after the month of the first date of study drug dosing; or
- Year is missing.

If severity or relationship of an AE to study drug is not recorded, the severity or relationship will be imputed as “severe” or relationship as “possibly related,” for analysis purposes. All efforts

will be made to ensure no missing severity or relationship of an AE to study drug prior to database lock finalization.

9.3.3.2 Concomitant Medications

If start date of a medication is missing, the medication will be considered to have started prior to the study. Such a medication may also be considered concomitant, depending on the stop date or lack thereof. If the stop date of a concomitant medication is missing, then the medication will be treated as ongoing. If the start date of a medication is missing, the stop date will be used to determine whether or not it is concomitant. Medications with other incomplete start dates or end dates will be imputed as follows:

Incomplete medication start date/time:

- If only have a YEAR, impute as Jan. 1.
- Else if only have YEAR and MONTH, impute as Day 1 of month.
- Otherwise missing, no imputation.

Incomplete medication end date/time:

- If only have a YEAR, impute as December 31.
- Else if only have YEAR and MONTH, then impute to last day of the month.
- Otherwise missing, no imputation.

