4.3.1.2 Glucocorticoid Dose Process and Documentation

Documentation of GC doses will be completed using eCRFs. If an adjustment in GC dose or change in distribution of daily doses is warranted, a new record will be recorded on the Prior and Concomitant Daily Glucocorticoids/Mineralocorticoids eCRF for each change.

At Weeks 24, 52 and 76 the eCRFs will record the total daily prescribed GC dose and will serve as the source for the Primary Efficacy Endpoint and GC-related change endpoints. For example, the recorded GC dose at Week 12 and the A4 assessment taken at Week 12 will be used to meet the Primary Efficacy Endpoint definition.

Based on the A4 assessment from each visit and aligning with the primary investigator's clinical judgement, the primary investigator will confirm if the GC dose level will be adjusted or maintained until the next clinic visit. For every visit with a potential adjustment in GC, the Key Glucocorticoid Dosing eCRF will record the A4 algorithm outcome (decrease, increase, maintain dose), whether the PI followed the algorithm's outcome (yes, no), reason for not following the outcome (clinical judgement, subject at physiologic dose), and the PI final decision (decrease, increase, maintain dose).

For subjects enrolled under protocol amendment 6 or earlier and prior to Week 24, the RTSM system will dispense a new GC regimen. For subjects enrolled under or after protocol amendment 7 or for visits after Week 24 for subjects enrolled under protocol amendment 6 or earlier, a new prescription will be written by the PI for the adjusted daily GC dose regimen and relayed to the subject to fill at their local pharmacy. An eCRF Glucocorticoid Medication – Received will record the date the subjects received/filled the new Sponsor-provided GC regimen and the day of first dose from the new regimen.

Reconciliation across eCRFs will be performed to ensure the accuracy of the GC dose data.

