8.3.20 Glucocorticoid Therapy

GC therapies are concomitant medications that fall under the Anatomical Therapeutical Chemical (ATC) classification is "Systemic Hormonal Preparations, Excl. Sex Hormones and Insulins" or "Glucocorticoids."

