8.3.20.3 Glucocorticoid Total Daily Dose in Hydrocortisone Equivalents

The total daily GC dose of a given subject is calculated as the sum of doses per day of concomitant GC therapies using the conversion in [Table 11](#), excluding stress dosing.

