8.3.20.4 Stress Event

A stress event is defined as an entry in the diary indicating a stress dose was taken or a record in the CM eCRF if the stress dosing was not recorded in the diary in a timely manner. Consecutive days of stress dosing are counted as a single stress event.

8.3.20.5 Cumulative GC Dose at Week 24

The cumulative GC dose from Study Day 1 to Week 24 is defined as:

- Sum of daily GC exposures (total daily dose multiplied by days on a regimen) from CM eCRF
- Sum of stress doses (HCe mg) (from CM eCRF where the indication for the stress dosing is “STRESS DOSE/DOSING”)

For subjects who discontinue study drug treatment prior to the Week 24 visit, the cumulative dose will be summed over the duration of Study Day 1 to the date of last dose of study drug.

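### Applied as written to glucocorticoid records, the SAP's medication-date rules count the old and new regimens together whenever a dose step has an incomplete date

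*SAP*

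**What the plan says.** Five parts of the SAP combine here.

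- **Records.** Under 4.3.1.2, when the GC dose or its distribution over the day changes, "a new record will be recorded on the Prior and Concomitant Daily Glucocorticoids/Mineralocorticoids eCRF for each change". Old and new regimens are therefore separate dated records.
- **Classification.** 8.3.20 says "GC therapies are concomitant medications that fall under" two named ATC classes.
- **Daily dose.** 8.3.20.3 defines the total daily GC dose, stress dosing aside, as "calculated as the sum of doses per day of concomitant GC therapies".
- **Cumulative dose.** 8.3.20.5 builds endpoint 3.2 from this component, to which stress doses are added: "Sum of daily GC exposures (total daily dose multiplied by days on a regimen) from CM eCRF".
- **Dates.** 9.3.3.2 has four relevant rules. For a missing stop: "If the stop date of a concomitant medication is missing, then the medication will be treated as ongoing". For a missing start: "If start date of a medication is missing, the medication will be considered to have started prior to the study". For a month-only start: "Else if only have YEAR and MONTH, impute as Day 1 of month". For a month-only stop: "Else if only have YEAR and MONTH, then impute to last day of the month".

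No sentence ends the old GC regimen when the new one begins, and 9.3.1 (efficacy data) has no GC date rule. 4.3.1.2 names an eCRF-recorded total prescribed dose for Weeks 24, 52 and 76 as the source for the primary endpoint and the GC change endpoints. It also promises reconciliation across eCRFs, without saying which date or dose prevails in a conflict.

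**The concern.** Moving starts early and stops late is a sound convention for deciding whether a drug was ever taken alongside study drug, because it errs towards inclusion. It does not suit consecutive maintenance regimens whose doses are then added. There it creates days on which the patient appears to take both the dose just left and the dose just started.

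The affected variable is what the trial measures. Endpoint 3.2 takes its daily exposures directly from these records. The primary mixed model uses baseline and Weeks 3, 6, 12, 18 and 24, and 4.3.1.2 names a separate recorded dose for only the last of these. The direction of the error depends on which date is incomplete. Overlap at a post-baseline visit makes a reduction look like an increase. A new record with no start date can be counted at baseline and make the reduction look too large.

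**Working it through.** **Inputs from the documents.** The four date rules (SAP 9.3.3.2); the summing rules (8.3.20.3, 8.3.20.5); steps of at most 5 mg/day HCe (protocol 4.1.4.3); entry range 30 to 60 mg/day (protocol 5.1.1); planning difference 5 mg/day, SD 6.9, 40 per group (SAP 6); 45 per group (protocol 9.2).

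**Assumptions for illustration.** One step from 35 to 30 mg/day on Day 15, over 168 days, with no stress dosing. Results are taken over 365 consecutive calendar dates for Day 1, because the month-only rules depend on where the step falls in the month.

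**Yardstick.** The SAP's power statement reproduces: 5 / (6.9 × √(2/40)) = 3.24; 3.24 − 1.96 = 1.28, which gives power of about 0.90 (0.893 with the noncentral t). It is used only to scale the errors below and is not disputed.

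**Cumulative dose.** The true total is 35 × 14 + 30 × 154 = 5,110 mg. Each overlap day after the step adds the old 35 mg. Each overlap day before it adds the new 30 mg.

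| Incomplete date | Overlap days in the window, mean (range) | Excess, mean (range) |
|---|---|---|
| Old stop, month only | 14.7 (0–30) | +10.1% (0 to +20.5%) |
| New start, month only | 10.5 (0–14) | +6.2% (0 to +8.2%) |
| Both, month only | 25.3 (0–31) | +16.3% (0 to +21.1%) |
| Old stop missing | 154 | +105.5% |
| New start missing | 14 | +8.2% |

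The extremes can be checked by hand.
- Both month-only, step on the 2nd of a 31-day month: 1 × 30 + 30 × 35 = 1,080; 1,080 / 5,110 = 21.1%.
- Both month-only, step on the 1st: the imputed dates are the true dates and the excess is zero.
- Old stop missing: 154 × 35 = 5,390; 5,390 / 5,110 = 105.5%.
- New start missing: 14 × 30 = 420; 420 / 5,110 = 8.2%.

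**Visit dose, if derived under 8.3.20.3.**
- Overlap at a post-baseline visit: 35 + 30 = 65 instead of 30. The change reads 65 − 35 = +30 instead of −5, an error of +35. One such value moves that visit's arm mean by 35/45 = 0.78 or 35/40 = 0.88 mg/day, which is 16 to 18% of the 5 mg planning difference.
- New start missing: baseline reads 65 instead of 35. With a correct Week 24 dose of 30, the change reads −35 instead of −5, an error of −30. One such value moves the arm mean by 30/45 = 0.67 or 30/40 = 0.75 mg/day (13 to 15% of 5 mg) in the opposite direction.

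**After the fix.** If the old regimen ends the day before the new one starts, overlap is zero. Only the uncertain step date remains. Setting the step to the first of the month gives at most 14 × 5 = 70 mg too little (−1.4%). Running the old regimen to month end gives at most 30 × 5 = 150 mg too much (+2.9%).

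**The case against.** The strongest reply is that 9.3.3.2 was never meant for GC dose. It sits under safety data and is about classifying medications. SAP 11.3 summarizes concomitant medications with glucocorticoids left out, and missing GC values have multiple imputation in 12.3.3.1. The intent may well be as described. However, 8.3.20 makes GC therapies concomitant medications, nothing exempts them, and no other date rule is given. The imputation in 12.3.3.1 fills absent visit doses and does not repair record dates.

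The second reply is that existing controls would catch the errors. This largely stands for gross cases. Steps are at most 5 mg/day, so a 30 mg rise at a visit where the Key Glucocorticoid Dosing eCRF records a decrease is visible. A 65 mg baseline exceeds the 60 mg entry limit and could contradict the randomization stratum. Protocol 10.7 requires full verification of data for primary and safety variables, and 4.3.1.2 promises reconciliation. A reader might infer from the permitted combination therapy that a program could not detect the overlap; these cross-checks show that it could. What is missing is a rule for what to do with a date that stays incomplete.

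The third reply is that the Week 24 dose has its own source. That is correct. For baseline and Weeks 3 to 18 the source is ambiguous: 4.3.1.2 names the recorded dose only for Weeks 24, 52 and 76, yet its own example refers to a recorded Week 12 dose.

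**Conclusion.** The point holds. Followed literally, the SAP double-counts GC dose on overlap days when a step has an incomplete date, unless the imputed date happens to be the true one. Endpoint 3.2 is directly exposed, at the sizes in the table. It is exploratory and outside the Type I error procedure of SAP 9.6. Exposure of the primary mixed model is conditional: it arises only if the baseline or Week 3 to 18 doses are derived under 8.3.20.3.

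Three stronger readings are tempting, and the documents do not support them.
- *The Week 24 dose in the primary endpoint is corrupted.* It is taken from the eCRF-recorded prescribed dose. Only an inflated baseline could distort the Week 24 change.
- *The bias runs in a known direction between arms, because doses change more often on active drug.* The first reduction depends on Day 1 A4 in both arms, and the algorithm also calls for increases, so a placebo subject reduced and then re-escalated generates records too. The two mechanisms also have opposite signs.
- *The trial will suffer a material error.* The number of incomplete GC dates is not given, and the per-subject shifts above assume one uncorrected case.

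The case for acting is that a stated rule gives a wrong answer and the correction is simple.

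**What to change.** Before database lock and unblinding, amend the SAP as follows.

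1. Limit 9.3.3.2 to non-GC medications.
2. For background GC, let each new maintenance regimen close the previous one on the day before it starts.
3. Take an incomplete step date from the Glucocorticoid Medication – Received eCRF where that form exists. 4.3.1.2 describes it for Sponsor-provided regimens, so it may not cover subjects on investigator-prescribed GC. For them, use the dose-adjustment telephone contact or the Key Glucocorticoid Dosing eCRF. Impute only when none of these gives a date.
4. Sum GC records only when they are identified as concurrent combination therapy.
5. State in 4.3.1.2 that the baseline and Week 3 to 18 doses come from the eCRF-recorded prescribed dose where available, and say which source prevails when eCRFs disagree.

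The cost is SAP wording and a few lines of derivation code, with no new data collection. Reporting the number of GC records with incomplete dates by arm would show whether the issue mattered.

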9.4 Primary Analyses and Data Monitoring

The primary efficacy analysis will be conducted when all subjects complete the Week 24 visit of the Placebo-Controlled Treatment Period and the data has been hard-locked for analysis. The Final Analysis will occur after the last subject has completed the Week 76 visit or if the study is discontinued by the Sponsor.

An external, independent data safety monitoring board (DSMB) will review the available safety data (both blinded and unblinded) from this study periodically. The DSMB will advise the Sponsor of any trends or safety issues that may impact the study or study subjects and provide recommendations to the Sponsor if needed.

9.5 Multicenter Considerations

This trial will be conducted at approximately 75 study centers in the United States, Europe, and other regions. Data from all study centers will be pooled for efficacy and safety analyses.

Because the number of subjects at each center is likely to be small, no analyses will be performed by center.

9.6 Type I Error Control

Type I Error control for the Secondary Efficacy Endpoints will be achieved by hierarchical testing. If the Primary Efficacy Endpoint is met, then Secondary Efficacy Endpoints displayed in [Table 5](#) will be evaluated using the Hochberg (1988) closed test procedure with an alpha of 0.05.

9.7 Examination of Subgroups

Subjects will be categorized into the following common subgroups for the purposes of evaluating the Primary and Secondary Efficacy Endpoints.

- Sex (Male, Female)
- Baseline GC dose in HCe
 - < 40 mg/day, \geq 40 mg/day
 - < 35 mg/day (For endpoint 2.2 and 3.7 only)
- Baseline A4 levels (A4 \leq ULN, A4 $>$ ULN)

In addition, all potential subgroup x subgroup combinations are also pre-specified. If the primary analysis is positive, exploratory subgroup analysis for age, race, ethnicity, and region will be used to further evaluate the Primary and Secondary Efficacy endpoints.

Comparisons will only be provided for subgroups where each subgroup has at least 10 subjects. Additional subgroups specific to only select endpoints are specified in the appropriate section in the SAP.

10 STUDY SUBJECTS

10.1 Subject Enrollment and Disposition

10.1.1 Screened and Enrolled Subjects

Screened and enrolled subjects will be summarized enrolled by country and by investigator for treatment each treatment group and overall.

Screening, enrollment, and disposition will be summarized for all screened subjects. Percentages will be based on total subjects who enrolled the study. Disposition will also be summarized for all subjects in the ITT analysis set. The percentages will be based on total subjects who were randomized in the study. A subject listing will be provided with the above information, as well as geographic region, country, and site ID for subjects who were screen failures and for subjects enrolled in the study.

10.1.2 Randomized Subjects

Dispositions of randomized subjects will be summarized by treatment group and overall for the Placebo-Controlled Treatment Period and the Open-Label Treatment Period.

A listing of disposition will be provided for all randomized subjects. A separate listing will present subjects who are excluded from SAF, mITT, PP, PK, and/or DXA analysis sets, along with reasons for the exclusions.

10.2 Protocol Deviations

Protocol deviations will be listed by deviation type (e.g., major) and category (e.g., noncompliance with study procedures or restrictions). All deviations will be identified prior to database lock and will be summarized and presented in listing(s); listings will include flags for deviation type (major or minor). Major protocol deviations are defined per *Guideline for Industry: Structure and Content of Clinical Study* from International Council for Harmonisation (ICH E3) guidance. Major analysis protocol deviations include, but not limited to:

- Randomized subjects who did not satisfy efficacy inclusion and exclusion criteria,
- Randomization error,

- Subjects who received the wrong tildacerfont dose,
- Subjects who received an excluded concomitant treatment or medication,
- Subjects who are less than 80% compliant with aggregate study medication measured by pill count or by e-diary

All protocol deviations and major protocol deviations will be summarized by deviation category and type. In addition, a listing of all deviations and major protocol deviations will be provided.

10.3 Demographics and Baseline Characteristics

Demographics and baseline characteristics will be summarized and listed for all randomized subjects (ITT).

10.3.1 Demographics

Demographic characteristics will include age, age category, sex, females with child-bearing potential, race, and ethnicity, type of CAH diagnosis, and time since CAH diagnosis. A subject listing of demographics will be provided.

10.3.2 Baseline Characteristics

The following baseline characteristics will be summarized. They will be listed in subject listings in the following categories: CV risk assessments; glucocorticoid regimen; selected serum hormones; and TART(s)

10.4 Medical History

Medical history and CAH history will be summarized by randomized treatment group for all enrolled subjects. Individual subject listings will include subject identification number and randomized treatment/dose level (if a subject is randomized), along with general history and CAH history data collected from eCRF, for all enrolled.

10.4.1 General Medical History

General medical history, besides CAH, will be mapped to preferred terms and system organ classes using the Medical Dictionary for Regulatory Activities (MedDRA®) Dictionary (version 23.0). General medical history will be summarized by system organ class (SOC) and preferred

term (PT). A subject listing of general medical history will include start date/end date, verbatim medical history term, SOC, PT, and ongoing status.

10.4.2 Congenital Adrenal Hyperplasia History

10.4.2.1 Signs and Symptoms

The most bothersome signs and/or symptoms of CAH will also be summarized. Signs and/or symptoms of CAH will be included in a subject listing.

10.4.2.2 Glucocorticoid History

The Baseline GC dose level in HCe, the duration (years) on the current background GC therapy, GC therapy medication(s), reasons for change to the current background GC therapy (if changed therapy) will be summarized for all enrolled subjects. A subject listing will include all summarized variables, as well as any higher/lower dose of GC during adulthood, reason to reduce/increase to the current GC dose.

10.4.2.3 Hospital and Stress Dosing History

Hospitalization and stress dosing history will be summarized separately and will include the frequency and percentage of subjects with at least one hospitalization for adrenal insufficiency/crisis in the past 5 years, at least one hospitalization for adrenal insufficiency/crisis in the past 12 months, and/or at least one stress dosing event in the past 12 months. A subject listing will be included.

